## 1.0 Study Summary

Study Title	An Open-Label, Single- and Multi-Dose Study to Evaluate the Relationship between the Pharmacokinetics, Pharmacodynamics, and Clinical Outcomes of Atomoxetine in CYP2D6 Extensive, Intermediate, and Poor Metabolizers in Children with Attention Deficit/Hyperactivity Disorder
Study Design	This is a non-randomized, un-blinded, exposure escalation efficacy trial of the effects of atomoxetine in children with attention deficit/hyperactivity disorder (ADHD).
Primary Objective	
 
1. To investigate the effect of genetic variability on the pharmacodynamics of ATX by evaluating biomarkers of inhibition of the drug target, the norepinephrine re-uptake transporter, following ATX exposure control.
 
2. To explore how changes in pharmacodynamic markers correspond to clinical response to medication.
 

Secondary Objective(s)	
 
1. To establish the relationship between ATX systemic exposure, inhibition of the norepinephrine uptake transporter, and therapeutic response
 
2. To determine global baseline patient characteristics differences between ATX responders and non-responders.
 
3. To explore how baseline oral microbiome make-up influences clinical outcomes and to describe changes in the oral microbiome with ATX therapy.
 
4. To refine the iGO-PK ATX dosing algorithm.
 
5. To evaluate comprehension of the study procedures by study participants and their families when an illustrated study booklet is supplied with a consent form.
 
6. To validate a urinary CYP2D6 phenotype biomarker.
 

Research Intervention(s)/ Investigational Agent(s)	Atomoxetine – a norepinephrine reuptake transporter inhibitor which is FDA approved for the treatment of ADHD in children. iGO-PK dosing algorithm – a dosing algorithm to normalize atomoxetine exposure regardless of CYP2D6 genotype.

SHORT TITLE: ATX-PBPK-PD-Clinical Outcomes (U54)

IND/IDE #	NA
Study Population	Children, both males and females between the ages of 6-18 with ADHD or a high likelihood of having ADHD, electing to receive care at Children's Mercy Hospital and Clinics and children enrolling in the CMH&C ADHD Summer Treatment Program (STP).
Sample Size	Target enrollment of 160 research participants, in anticipation of 120 participants completing the research study.

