### 2.2 Hypotheses to be Tested:

- Hypothesis 1: Genetic variability in the *SLC6A2* gene is associated with variability in 1) concentration-time curves of DHPG and 2) pupil size changes, when evaluating tonic and phasic data.
- Hypothesis 2: Variability in pharmacodynamics markers, i.e. plasma DHPG and pupil size changes, are associated with clinical response to atomoxetine.
- Hypothesis 3: The atomoxetine response cohorts (i.e. response versus non-response and tolerant versus non-tolerant) will have differing global baseline characteristics, such as age, gender, ethnicity, ADHD subtype, genetic polymorphisms, etc.

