#### 4.2 Primary Safety Endpoints

Participant baseline health, including behaviors, will be recorded at Research Visit 1 with a physical exam, baseline electrocardiogram, medical history, and concomitant medication history. Additionally, baseline health and behavior data will be captured at the Intake Visit with the Study Physician. Adverse events will also be closely monitored. These are defined by Children’s Mercy Hospital Reportable Events Research Policy and Procedures as “untoward or unfavorable occurrences in a human subject, including an abnormal sign [e.g., abnormal physical exam or laboratory finding], symptom, or disease, temporally associated with the subject’s participation in the research, whether or not considered related to the subject’s participation in the research.” Additionally, an adverse event is also defined as behaviors or symptoms that occur with increased frequency or severity as consequence of the subject’s participation in the research study.

Both types of adverse events will be documented in this study. Adverse events are reported in many ways in this study. These include but are not limited to: emails to study coordinators/clinical trial manager, phone calls on study cell phone, phone calls to ADHD Clinic or Developmental and Behavioral Clinic, reported to study physician at clinic visit, reported on Medication Side Effects questionnaires, reported at research visits when asked, or via a Cerner notification of admission to the hospital to the study physician. Additionally, adverse events will be assessed and documented at Research Visit 2, Research Visit 3, Research Visit 4, 6-week Visit, 12-week Visit, and 18-week Visit.

Adverse events will be categorized and reported to the IRB as outlined in CM Policy regarding adverse events. These events will be documented consistently, regardless of how they were reported. This includes the delegation of an individual member of the study personnel to handle all adverse event reporting. All adverse events will be recorded at all research visits and in between visits as needed on the Adverse Event CRF kept in the subject’s study binder.

In addition, subjects will be classified based on their tolerance of ATX. A participant is considered tolerant of ATX if the side effects did not lead to discontinuation of ATX therapy. A participant is considered intolerant of ATX if the side effects lead to the discontinuation of medication and withdrawal of a subject from the study.

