### **8.2 Target Participants**

The research proposal targets 160 participants who are expected to be enrolled and screened. The target number of subjects needed to complete research procedures is 120. Participants who complete at least Research Visits 1-3, the Intake Visit, and the 6-Week Visit with the Study Physician will be considered to have "partially completed" the study. Completion of these visits will include obtaining baseline measurements, confirmation of eligibility, single and steady-state PK and PD measurements, and at least one post-treatment clinical response assessment. Since data from these participants will meet the study aims, those who partially complete the study will be counted toward the 120.

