## 20.0 Data Management

### 20.1 Data Analysis Plan

#### Population to be Analyzed:

- The pharmacokinetic population will consist of all participants with sufficient plasma concentrations for calculation of all pharmacokinetic parameters.
- The pharmacodynamic population will comprise of all patients with sufficient DHPG plasma concentrations, adequate data from pupil dilation and eye-tracking measurements, and cardiovascular measures (heart rate and blood pressure). Additional metabolites analyzed via metabolomics platform will also be analyzed (as discussed below).
- All participants who meet criteria for determination of both pharmacokinetic and pharmacodynamic parameters and have at least partially completed the study will be evaluated for pharmacodynamic linked clinical outcomes analysis. A partial completion is any participant where at least Research Visit 1, Research Visit 2, Research Visit 3, Intake Visit with Physician, and 6-week Visit with Study Physician have been completed. Clinical outcomes will be analyzed in four ways:
  - Response: responder vs. non-responder
  - Toxicity: tolerant vs. non-tolerant
  - Adherence: low, medium, and high
  - Adverse event reporting
- In addition, all participants for which demographic and background characteristics and concomitant medication history were collected will be analyzed.
- All completed and returned U54 Study Booklet questionnaires and surveys will be used to assess the effectiveness of the U54 Study Booklet in study comprehension. Feedback from the survey will be compiled for analysis.

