#### Pupillometry Analysis:

Changes in performance during Posner Cuing Task will be measured as a function ATX exposure and  $C_{max}$  concentrations. Pupil size will be measured during two types of activities: localization and discrimination tasks. Pupil size differences during localization tasks report on the individuals' baseline (tonic) release of norepinephrine. This corresponds to endogenous, or volitional attention. Pupil size differences during discrimination tasks is a composite of the individuals' baseline (tonic) and situational (phasic) release of norepinephrine. Currently it is unclear whether tonic, phasic, or both are impaired in individuals with ADHD.

Cardiovascular Marker Analysis:

Changes in heart rate will also be measured as a function ATX exposure and  $C_{max}$  concentrations. One side effect of ATX that is directly related to the pharmacodynamics of the drug is an increased heart rate due to increased concentration of norepinephrine in blood. We would like to understand the extent of this side effect as a function of increased systemic ATX exposure and  $C_{max}$ . By studying these two components, we will be able to distinguish ATX drug action in central and peripheral nervous systems.

Pharmacodynamic Changes Correlated with change in NICHQ Vanderbilt Assessment Scales:

All changes markers of pharmacodynamic action will be correlated with whether a child is classified as a responder or non-responder; and tolerant or intolerant (see Clinical Outcomes below for details). Extent of adherence will be used as a confounding factor in both of these analyses.

Clinical Outcomes:

Determine and document participant response to ATX therapy:

- Responders will be defined as:
  - Participants, who after approximately 18 weeks of continuous treatment with ATX, demonstrate  $\geq 40\%$  reduction of baseline ADHD symptom score;
  - OR the Clinical Global Improvement rating is 1 or 2 (Very Much Improved or Much Improved).
- Non-responders will be defined as:
  - Participants, who after approximately 18 weeks of continuous treatment with ATX, demonstrate  $< 40\%$  reduction of baseline ADHD symptom score, AND the Clinical Global Improvement score  $\geq 3$ .
  - Participants who discontinue ATX prior to the planned end of study (18 weeks) due to perceived lack of efficacy despite dose escalation.

Determine and document participant tolerance of ATX therapy:

- ATX intolerant participants are:

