  - Participants who present with side-effects that significantly interfere with daily functioning or outweigh therapeutic benefit (CGI Efficacy Scale categorization)
  - Participants who must discontinue ATX for any of the following reasons: AST or ALT three times the upper limit of normal (ULN) for age, alkaline phosphatase five times the ULN, total bilirubin two times ULN, QT prolongation or dysrhythmia, hypertension (systolic or diastolic BP above 95% for age), tachycardia (HR above 95% for age)

Parent and teacher responses for the NICHQ Vanderbilt Assessment Scales will be obtained at baseline and  $\pm$  2 weeks of 6-week Visit with Study Physician, 12-week Visit with Study Physician, and 18-week Visit with Study Physician. If questionnaires are returned outside of this window, or are unreturned, these will be considered, "missing data." Determination of response, i.e. responder vs. non-responder, will be done using parent responses to questionnaires. Teacher response to questionnaires will also be analyzed to evaluate symptom reduction in a secondary setting. Partial return of teacher questionnaires are still useful in that these data may be used to correct for bias in parental response.

Questionnaires conducted at baseline and at either 18-week visit with Study Physician or a Research Visit will be analyzed for change pre- and post-intervention. These include: BRIEF – parent, SCT, SCARED, CBCL, and School Intervention Questionnaire.

Statistical analyses of clinical response in the population studied will be performed by The Division of Health Services and Outcomes Research at the Children's Mercy Hospital, Kansas City, MO. SAS version 9.4 (SAS, Cary, NC, USA) and R (The R Foundation) will be used to determine if ATX responders and non-responders can be differentiated by a subset of patient specific covariates.

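### Read literally, the analysis plan assesses tolerance and adverse events only in PK- and PD-evaluable partial completers, leaving out children who stop early for side effects

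*Combined protocol and SAP*

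**What the plan says.** All references are to the combined protocol and SAP.

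- **Restricted set (20.1, Population to be Analyzed).** Participants who meet the criteria for "both pharmacokinetic and pharmacodynamic parameters and have at least partially completed the study will be evaluated for pharmacodynamic linked clinical outcomes analysis". Partial completion means that Research Visits 1, 2 and 3, the Intake Visit and the 6-week visit were all completed. The same bullet says clinical outcomes will be analysed in four ways: response, tolerance, adherence and adverse event reporting.
- **Wider set (next bullet).** "all participants for which demographic and background characteristics and concomitant medication history were collected will be analyzed". Tolerance and adverse events are not named there.
- **Intolerance, Section 4.2.** A participant is "considered intolerant of ATX if the side effects lead to the discontinuation of medication and withdrawal of a subject from the study".
- **Intolerance, 20.1 Clinical Outcomes.** This covers listed laboratory and cardiovascular reasons for having to discontinue. It also covers "Participants who present with side-effects that significantly interfere with daily functioning or outweigh therapeutic benefit", with no requirement to stop drug.
- **Uses of tolerance status.** Hypothesis 3 in Section 2.2: "The atomoxetine response cohorts (i.e. response versus non-response and tolerant versus non-tolerant) will have differing global baseline characteristics". In 20.1, under the heading on correlation with the NICHQ Vanderbilt scales: "All changes markers of pharmacodynamic action will be correlated with whether a child is classified as a responder or non-responder; and tolerant or intolerant".
- **Withdrawn participants (16.2).** Their samples and data are saved for analysis, but no analysis or set is named.

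**The concern.** Neither definition of intolerance sets a minimum time on drug, and Section 16.1 anticipates withdrawal for adverse events without one. Entry to the restricted set does require time on drug. The event that makes a child intolerant can therefore be the event that keeps the child out of the set in which tolerance is assessed.

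Two analyses are at stake. The tolerant versus non-tolerant baseline comparison in Hypothesis 3 would lose its early intolerant cases. If a baseline characteristic predisposes children to early side effects, the intolerant children left in the set would be depleted of it and the contrast would be weakened. The adverse event summary would omit the same children. For both analyses the relevant data have been collected.

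**Working it through.** The plan states no tolerance rate, so there is no figure to reproduce. The check sets the passages side by side and then asks what can be said about size.

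**1. When a child can qualify.** Research Visit 3 needs two weeks of routine dosing and may take place any time before the 18-week visit (11.1). It is rescheduled if the child has not been compliant (11.2), so a child already off drug does not qualify through it. The 6-week visit has a window of plus or minus 2 weeks, so the earliest qualification is about 6 − 2 = 4 weeks after starting. If Research Visit 3 is still pending, the gap can run on towards the 18-week visit.

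**2. A worked case.** A child has the first dose at Research Visit 2, develops side effects, stops and is withdrawn at week 3.
- Section 4.2: intolerant.
- 20.1, restricted set: not a partial completer, so excluded.
- 20.1, next bullet: included for demographics, background and concomitant medication only.
- 16.2: data saved, analysis unspecified.
- 20.2: weighting or imputation to be considered, no set named.

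**3. Children who stop later.** The pharmacodynamic population also needs adequate DHPG, pupil, eye-tracking and cardiovascular data. A child who completes the visits but lacks usable pupillometry is outside the set too, whether or not the drug was tolerated.

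**4. Can the size be derived?** Let S be the number in the set, I the intolerant among them, E the dosed children outside it, and k the intolerant among E.
- Proportion in the set: I/S. Proportion in all dosed: (I + k)/(S + E).
- Difference, all dosed minus set: [E/(S + E)] × (k/E − I/S). It is zero when k/E = I/S. The set understates intolerance only if k/E is larger.
- Share of intolerant children lost: k/(I + k). This is above zero whenever k is, even if the proportion is unbiased.

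The documents supply none of S, I, E or k:
- *S.* Section 1.0: "Target enrollment of 160 research participants, in anticipation of 120 participants completing the research study". Section 8.2: "those who partially complete the study will be counted toward the 120". The 8.2 count depends on visits alone, whereas the 20.1 set also needs evaluable PK and PD data. If the target is met, 120 is a ceiling for S.
- *E and k.* 160 − 120 = 40 children are not expected to reach partial completion, but 8.2 describes the 160 as enrolled and screened. The 40 therefore include screen failures who were never dosed, and no split is given.
- *Attrition in 20.2.* 120 × 0.20 = 24 lost, leaving 96. That section does not say that 120 are dosed. A child who leaves after Research Visit 3 and the 6-week visit can be among the 24 and still be in the set.

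**5. Illustration on assumed counts only.** With I = 10, k = 0, 5 or 10 gives a lost share of 0/10 = 0%, 5/15 = 33% or 10/20 = 50%. These counts are invented to show how the loss behaves; they do not estimate it.

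**The case against.** The strongest reply is that the restriction was meant for something else. The bullet speaks of a pharmacodynamic-linked analysis, which does need PK and PD data, and the sentence listing four outcomes does not repeat the restriction. Section 4.2 and the Clinical Outcomes text classify subjects or participants without naming a set, and 16.2 keeps everyone's data. On that reading early stoppers were never to be excluded, and the fault is loose wording. This stands as a possible reading, but it leaves the gap open. If the set serves only the PD correlations, no visible passage names a population for tolerance, for adverse events or for the tolerance part of Hypothesis 3. The Clinical Outcomes methods describe responders against non-responders only.

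One might add that the wider bullet covers Hypothesis 3 variables such as age and gender. It does, but 20.1 plans only descriptive summaries of background and demographic characteristics and does not mention tolerance groups.

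Nor does any objective ask for a tolerance rate. That is correct, so the consequence rests on Hypothesis 3 and the adverse event summary rather than on a headline rate.

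Finally, the DSMB Charter and DSMB Protocol, listed in Section 32.0, were not supplied and may define a safety set. The conclusion is limited to the visible text.

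A reader might infer that safety oversight fails for these children. The documents do not support that. Adverse events are checked about two weeks after withdrawal (11.2, item 10), followed to resolution (16.2) and monitored by the DSMB (21.1).

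**Conclusion.** The point holds as a flaw in the literal text of 20.1: tolerance and adverse event reporting sit only under a set that a child can miss because of intolerance. It should be fixed before analysis; otherwise the analyst chooses the tolerance denominator after seeing the data.

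The size is unknown. A reader might be tempted to take 120 as the set and the other 40, or the 24 lost in 20.2, as early side-effect stops, and so compute how far intolerance is understated. The documents do not support this: 120 is at most a ceiling, the 40 include screen failures, and the 24 may include children who already qualify. Understatement of a tolerance proportion requires dosed children outside the set to be intolerant more often than those inside, and the documents give no such rate. Intolerance without discontinuation, which only the Clinical Outcomes definition allows, would keep some intolerant children in the set and make any bias smaller. Nor do the documents show that early stoppers were excluded on purpose.

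**What to change.** In 20.1, Population to be Analyzed:
- State that tolerance, adverse event reporting and the tolerant versus non-tolerant comparison of Hypothesis 3 are analysed in all children given at least one dose of study drug.
- Keep the PK- and PD-evaluable partial-completer set for the PD-linked analyses only.
- Report the number of dosed children outside that set, by reason.
- Reconcile the intolerance definitions in Section 4.2 and in 20.1 Clinical Outcomes so that one applies throughout.

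If the DSMB documents already define an all-dosed set, a cross-reference may be enough for the adverse event part.

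The cost is wording, since the data are already collected and retained. There are two drawbacks. Denominators will differ between the tolerance and PD-linked analyses. Children who stop before Research Visit 3 have no steady-state exposure data, so their intolerance cannot be related to steady-state exposure.

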#### Pharmacokinetics:

Estimation of the pharmacokinetic parameters and generation of the statistical analyses on the PK parameters will be performed by The Division of Clinical Pharmacology Toxicology & Therapeutic Innovation at the Children's Mercy Hospital, Kansas City, MO. Pharmacokinetic analyses will be conducted using Kinetica™ version 5.0 (ThermeElectron, Philadelphia, PA). Plasma ATX concentration versus time data will be curve fit using a peeling algorithm to generate initial polyexponential parameter estimates. Final parameter estimates will be determined from an iterative, nonlinear weighted least squares regression algorithm with reciprocal ( $1/y^2_{\text{calc}}$ ) weighting. Model-dependent pharmacokinetic parameters will be calculated from final polyexponential parameter estimates. Final model selection will be performed by evaluating the

goodness-of-fit criteria including; the objective function, Akaike & Schwartz criteria, standard deviations and coefficients of variation for the polyexponential parameters estimates and the correlation matrix detailing the degree of interdependence between the parameter estimates for each model. In the event that an insufficient number of post-peak ATX plasma concentration time points are available, a model-independent approach will be used and parameters of interest calculated using standard techniques. Specifically,  $C_{max}$  and  $T_{max}$  will be obtained by direct examination of the plasma concentration versus time profile. The area under the plasma concentration versus time curve during the sampling period ( $AUC_{0-n}$ ) will be calculated using the mixed log-linear rule and extrapolation of the AUC to infinity ( $AUC_{0-\infty}$ ) calculated by summation of  $AUC_{0-n} + Cp_n/\lambda_z$ , where  $Cp_n$  represents the final plasma concentration predicted from the fitted apparent terminal elimination phase and  $\lambda_z$  is the apparent terminal elimination rate constant. Model-independent pharmacokinetic parameters will then be calculated using standard (i.e., statistical moment theory) techniques. ATX metabolites *N*-desmethylatomoxetine (NDM-ATX), 4-hydroxyatomoxetine (4-OH-ATX) and hydroxyl-2-carboxylatomoxetine (OH-2-COOH-ATX) pharmacokinetics will be evaluated in a fashion analogous to that described for the parent compound.

The following PK parameters will be derived by non-compartmental analysis from plasma concentration data following a single dose study drug administration:

$C_{max}$	Peak plasma concentration determined from the observed data
$T_{max}$	Time to observed maximum drug concentration
$AUC_{0-\tau}$	Area under the plasma concentration versus time curve, determined by log-linear trapezoidal estimation, to the 12 or 24 hour time point (depending on CYP2D6 AS designated study design).
$AUC_{0-\infty}$	Area under the concentration versus time curve to infinity, determined by log-linear trapezoidal estimation $AUC_{0-\tau} + C_{\tau}/k$ Where $k$ is the elimination rate constant defined as the negative slope following maximum concentration determined by least squares regression from terminal phase data.
$T_{1/2}$	Terminal half-life determined by quotient $0.693/k$
$CL/F$	Oral clearance determined by quotient dose/ $AUC_{0-\infty}$
$Vd/F$	Terminal phase volume of distribution determined by Dose/ $k \cdot AUC_{0-\infty}$

fm	Fraction of drug metabolized through different pathways of biotransformation
----	--

The following PK parameters will be derived by non-compartmental analysis from plasma concentration data following chronic dosing to steady-state of study drug:

$C_{max,ss}$	Peak plasma concentration determined from the observed data at steady-state
$T_{max, ss}$	Time to observed maximum drug concentration at steady-state
$AUC_{0-\tau,ss}$	Area under the plasma concentration versus time curve, determined by log-linear trapezoidal estimation, to the 12 or 24 hour time point (depending on CYP2D6 AS designated study design).
$T_{1/2}$	Terminal half-life determined by quotient $0.693/k$
$CL/F_{ss}$	Oral clearance determined by quotient dose/ $AUC_{0-\infty}$
$Vd/F_{ss}$	Terminal phase volume of distribution determined by Dose/ $k \cdot AUC_{0-\infty}$

iGO-PK Model Update: The current iGO-PK Model (Version 1.0) uses ATX pharmacokinetic data from 24 pediatric participants (Brown et al., 2016). Since the building of Version 1.0, more ATX pharmacokinetic data has been collected from studies conducted at Children's Mercy Hospital (IRB# 16010069) and this current study. The data will be used to update and refine the iGO-PK model when it has been determined that sufficient new data has been collected. This determination will be made by the Principal Investigators and other Co-Investigators.

Pharmacodynamics:

Estimation of the pharmacodynamics parameters and generation of statistical analyses will be performed by The Division of Clinical Pharmacology, Toxicology & Therapeutic Innovation at the Children's Mercy Hospital, Kansas City, MO. An indirect model of pharmacodynamic changes, using change in plasma DHPG as a function of systemic plasma ATX concentration will be evaluated using Phoenix NLME (Certara, Princeton, NJ, USA), NONMEM (Icon, Dublin, Ireland), MATLAB (Natick, MA, USA), SAS version 9.4 (SAS, Cary, NC, USA), and R (The R Foundation). Concentration changes in DHPG as a function of change in systemic ATX levels will be fit to an indirect model (Equation A). Pharmacodynamic parameters  $k_{in}$ ,  $k_{out}$ ,  $I_{max}$ , and  $IC_{50}$  will be estimated for each metabolite studied using a nonlinear mixed effects model to take into account variability of pharmacodynamic marker change within the study population. Statistical regression models will be constructed to determine which patient covariates are

predictive of pharmacodynamic response. A maximal effect ( $E_{max}$ ) model describing the relationship between ATX concentration and pharmacodynamic effect will also be assessed in this study (Equations B and C). Models will be compared using statistical tests (Sum of Squares, Loglikelihood, AIC, standard error of estimates, and distribution of residuals). Changes in ATX  $C_{max}$  and  $AUC_{0-\infty}$  will also be plotted against pupillometry and eye-tracking data gathered when testing participants with localization and discrimination tasks. To describe the relationship between attentional orientating as function of ATX exposure, the data will be regressed both linearly and non-linearly and best of fit statistics (Akaike Information Criteria and Bayesian Information Criteria) will be employed to determine the most appropriate model.

